#### **4.6 Device/Study Exposure and Index Procedure**

Extent of exposure to study device during index operation in minutes will be calculated as:

$$(\text{device stop date/time} - \text{device start date/time})$$

Where device interruptions will be accounted for within the calculation.

Post index operation follow-up duration in days will be calculated as:

$$(\text{study exit date} - \text{device stop date}) + 1$$

Total study duration in days will be calculated similarly as:

$$(\text{study exit date} - \text{Informed consent form (ICF) date}) + 1$$

A summary of device/study exposure and index procedure information will be provided by treatment.

### **5 STATISTICAL ANALYSIS METHODS**

#### **5.1 General Considerations**

Unless otherwise specified, all statistical analyses will be performed on the mITT population.

In general, summary statistics (n, mean, SD, median, minimum, and maximum for continuous variables, and number and percentage of subjects in each category for categorical variables) will be provided by treatment. All summary tables will be based on the observed data unless specified otherwise. Source data for the summary tables and statistical analyses will be presented as subject level data listings.

The two-sided significance level of 5% is used for the hypothesis testing, unless specified otherwise.

Fixed sequence testing procedure will be utilized to compare the effectiveness of the treatment vs control in the following order:

Primary endpoint → Key secondary endpoint → Additional Secondary endpoints (24hr CTD → platelet transfusions → PRBC transfusions → UBPB events by class → surgical re-exploration for excessive bleeding → fatal perioperative bleeding event)

The significance for the secondary endpoints will only be considered if the primary endpoint is declared statistically significant and the p-value of the previous endpoint is less than 5%, otherwise, the testing procedure stops, and all the subsequent p-values will be nominal.

## 5.2 Analysis of the Primary Effectiveness Endpoint

The primary effectiveness endpoint is a hierarchical composite endpoint with three components ranked in descending order of clinical importance as follows:

1. Fatal perioperative bleeding event (occurring within 48hrs post index procedure)
2. Moderate, severe, or massive perioperative bleeding events according to UDPB classification (UDPB  $\geq 2$ ) (Dyke 2014)
3. 24-hour chest tube drainage (CTD) (mL) following surgery.

The hypothesis for the primary effectiveness endpoint will be tested using Finkelstein-Schoenfeld test (Finkelstein et al 1999). In constructing the test, “wins”, “losses”, or “ties” for all pairs of subjects in sequential comparisons according to the hierarchical order of the components of the primary composite endpoint.

Specifically, let the primary effectiveness endpoint  $Y = (y_1, y_2, y_3)$ , we evaluate win/loss for all subject pairs  $(i, j)$  as follows:

**Step 1:** Pair  $(i, j)$  is evaluated at the first component: fatal perioperative bleed occurring within 48 hours of the index procedure, with a binary (yes/no) outcome. It requires one subject not to experience the event and the other subject to experience the event in order to declare a “winner”, i.e.,

the subject  $i$  wins if  $y_1[i]=\text{no}$ ,  $y_1[j]=\text{yes}$ ; loses if  $y_1[i]=\text{yes}$ ,  $y_1[j]=\text{no}$ .

Otherwise, this is a tie for the pair in the first component and move to Step 2

**Step 2:** The second component - moderate, severe, or massive perioperative bleeding events according to UDPB classification  $\geq 2$  is also a binary (yes/no) outcome and follows the same process as step 1 for determining a win ( $y_2[i]=\text{no}$ ,  $y_2[j]=\text{yes}$ ) or a loss ( $y_2[i]=\text{yes}$ ,  $y_2[j]=\text{no}$ ) for the subject  $i$ . Otherwise, this is a tie at the second level and move to Step 3.

**Step 3:** The third component is 24-hour chest tube drainage (mL) following surgery. This is a quantitative (continuous) outcome where a lower drainage is better and therefore the subject with less drainage is declared the winner, i.e.,

the subject  $i$  wins if  $(y_3[i] < y_3[j])$ ; loses if  $(y_3[i] > y_3[j])$

Otherwise, they tie on the primary effectiveness endpoint.

## 5.2.1 Primary Hypotheses

The null hypothesis for the primary composite endpoint is represented by:

$H_0$ : The distribution of the components is the same in the two treatment groups

The alternative hypothesis for the primary composite endpoint is represented by:

$H_A$ : For at least one component, the distribution is different between the treatment groups

The null hypothesis for the primary composite endpoint can also be represented by the following equations:

$$H_0: \pi_{1,DS} = \pi_{1,SOC} \text{ AND}$$

$$\pi_{2,DS} = \pi_{2,SOC} \text{ AND}$$

$$\mu_{3,DS} = \mu_{3,SOC}$$

The alternative hypothesis for the primary composite endpoint is represented by:

$$H_A: \pi_{1,DS} \neq \pi_{1,SOC} \text{ OR}$$

$$\pi_{2,DS} \neq \pi_{2,SOC} \text{ OR}$$

$$\mu_{3,DS} \neq \mu_{3,SOC}$$

where  $\pi_{1,DS}$  and  $\pi_{1,SOC}$  are the rates for fatal bleeding with DrugSorbTM-ATR (DS) and Control (SOC), respectively;  $\pi_{2,DS}$  and  $\pi_{2,SOC}$  are the rates for UDPB  $\geq 2$  with DrugSorbTM-ATR (DS) and Control (SOC), respectively; and  $\mu_{3,DS}$  and  $\mu_{3,SOC}$  are the mean 24hr CTD with DrugSorbTM-ATR (DS) and Control (SOC), respectively.

## 5.2.2 Primary Effectiveness Analysis

The primary effectiveness analysis will be performed on the mITT population. It consists of hypothesis testing based on Finkelstein-Schoenfeld test (Finkelstein et al 1999) and the win ratio estimates following the unmatched win ratio method (Pocock 2012).

### 5.2.2.1 Significance Test

The primary hypothesis will be tested at the two-sided significance level of 0.05 using Finkelstein-Schoenfeld test statistics (Finkelstein et al 1999). All pairs of subjects are compared, regardless of the treatment groups, and a score  $W_{ij} = 1, -1$  or 0 is assigned to the pair  $(i, j)$  depending on whether subject i was a winner, a loser, or the comparison was inconclusive.

The test statistic is  $T = \sum_i D_i W_i$ , where  $D_i$  is the indicator variable for the treatment and  $W_i = \sum_j W_{ij}$ . Under the null distribution of no treatment effect, T is asymptotically normally distributed with mean 0 and variance  $\frac{n*m}{N*(N-1)} * \sum_i W_i^2$ , where n and m are the sample size for the treatment and control group respectively, and  $N = n + m$ .

Therefore, a significance test based on the standardized T statistic denoted by Z-statistics will be used to test the null hypothesis. The p-value will be provided and compared at the significance level of 0.05.

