3.0	01-21-2022	
 • Language around inclusion criteria #3 has been updated to allow enrollment of patients undergoing CT surgery with CPB “within two days following ticagrelor discontinuation (date of last dose = day 0).” The change to the inclusion criteria itself is reflected in the protocol Synopsis and Section 4.4.1 Inclusion Criteria. References to this time-point have been updated throughout the remainder of the text where relevant • All references to prior eligibility timeframe of “48hrs since last ticagrelor dose” have been updated to “within two days of ticagrelor discontinuation” through-out the protocol to ensure consistency with the above • Language around exclusion criteria #1 has been revised to exclude those patients who are undergoing “cardiothoracic surgery occurring 3 or greater following ticagrelor discontinuation.” This update has been made within the protocol Synopsis and Section 4.4.2 Exclusion Criteria • The screening period described in Table 6 (Schedule of Assessments) has been updated to “Up to two days prior to the day of operation,” to maintain consistency with the revised Inclusion Criteria #3 • The primary analyses of the trial will be performed on the modified intent-to-treat (mITT) population rather than the intent-to-treat (ITT) population, with supplemental analysis to be performed on the ITT population. This language has been updated in the protocol Synopsis and Section 11.2 Analysis Populations accordingly
4.0	08-10-2022	
 • Geographic location of study sites has been updated to include both the US and Canada (Synopsis and Section 1.1) • The term “response rate” has been revised to “effect size” in Section 11.1 Statistical Power and Sample Size Determination • Additional clarifying language added around the ITT,

		
MIITT, PP, and Safety Populations, and their planned analysis (Synopsis and Section 11.2)
 
 Language around stratification of the Win Ratio analysis by study site and surgery type has been removed from Section 11.3 Effectiveness Analysis Language around planned subgroup analyses has been moved to a separate section (Section 11.4 Subgroup Analysis) Typographic error has been corrected in Section 11.6 Treatment of Missing Data Language incorrectly referring to subgroup analysis of safety results in Section 11.7 Safety Analysis has been removed

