This study is a prospective, multi-center, double-blind, randomized pivotal trial to evaluate the safety and effectiveness of the DrugSorb™-ATR device to reduce postoperative bleeding as measured by a composite endpoint of: fatal perioperative bleeding (occurring within 48hrs of the index operation), moderate, severe, or massive bleeding (UDPB ≥ 2), and 24-hour chest tube drainage in patients undergoing cardiothoracic surgery requiring CPB within two days of ticagrelor discontinuation. Subjects will be randomized in a 1:1 ratio to either standard of care (SOC) alone (control arm) or standard of care plus intraoperative ticagrelor removal with DrugSorb™-ATR integration in the CPB circuit (investigational arm). In the control arm a sham device that is not actively connected to the CPB circuit will be placed in the identical location as the DrugSorb™-ATR device in the investigational arm, with the entire set-up covered by a drape to maintain the

blind. Subjects will be followed out to 30 days after the surgical procedure for assessments of adverse events (AE) and survival.

Prior to randomization, subjects will be stratified based on a) site, and b) type of planned cardiothoracic surgery [either CABG alone, or all other surgeries (including but not limited to combination cardiac procedures, and aortic interventions)]. Stratification is intended to control for confounding effects arising from differing institutional practices and from procedure-specific CPB duration (i.e., device exposure – treatment duration) and bleeding risk.

Number of subjects:

Up to 140 subjects will be randomized into the study (70 into each arm).

Number of sites:

Approximately 30 investigational sites in the US and Canada will participate in the study.

Subjects must meet all inclusion criteria to be eligible to participate in the study. Subjects meeting any of the exclusion criteria are not eligible to participate in the study.

Inclusion criteria:

1. Males and females aged ≥ 18
2. Written full informed consent
3. Cardiothoracic surgery requiring CPB within two days of ticagrelor discontinuation (**last day of completed ticagrelor treatment** = day 0):
 - CABG alone
 - Valve repair or replacement
 - Combination surgery (i.e., CABG + valve operation)
 - Aortic surgery

Exclusion criteria:

1. Cardiothoracic surgery occurring 3 days or greater following ticagrelor discontinuation
2. Heart-lung transplant procedures

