Pre-randomization stratification based on a) study site, and b) planned type of cardiothoracic operation will address potential confounding variables that may not be fully controlled in the randomization process. Stratification by site is intended to control for institutional differences in standard practices, such as transfusion and re-operation protocols. Stratification by the type of planned operation will separate subjects undergoing CABG-alone from those undergoing all other cardiothoracic surgeries. The category of “all other” cardiac surgeries includes combination cases (e.g., CABG + valve, double valve, etc.) and ascending aortic interventions. Compared to CABG-alone, these operations have a significantly different profile in regards to bleeding risk and procedure/CPB duration. This distinction is also important since device exposure is directly related to the amount of time spent on CPB. Details of the statistical considerations around the endpoints discussed above will be provided in **Section 11**.

In summary, the objective of the randomized, double-blind investigation outlined in this protocol will be to examine the ability of DrugSorb™-ATR (a non-pyrogenic, sterile, single-use device designed to remove the small hydrophobic drug, ticagrelor) to reduce postoperative bleeding compared to current standard of care. Measurements of drug removal will also be performed to establish that bleeding reductions are related to reductions in ticagrelor levels. The safety of the device in this setting will be assessed by systematic capture of all AEs at the CGP level.

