6.2. Subject Randomization

All subjects will be prospectively randomized via an Interactive Voice/Web response (IxRS) system. Randomization must occur prior to the start of the cardiothoracic surgery procedure requiring CPB, but only after subject eligibility criteria is confirmed and written informed consent is provided by the subject or the subject's designated proxy. Subjects will be randomly assigned in a one to one (1:1) ratio to either the control arm (SOC) or the investigation arm (SOC + DrugSorb™-ATR device).

To ensure even distribution of subjects among the factors most likely to impact the primary and secondary outcomes they will undergo pre-randomization stratification based on study site (to account for different institutional protocols for bleeding and transfusion management), and type of surgery (isolated CABG – which generally has shorter CPB time, vs. all other cardiothoracic surgeries including combination cases – which generally require longer CPB times). Neither the investigator nor the subjects will be told their assignment prior to surgery. See below (**Section 6.3.1**) for details of the randomization assignment. A copy of the randomization assignment will be maintained in a confidential file maintained by the Randomization and Unblinding Administrator. If the subject withdraws consent following randomization but prior to surgery, the reason for failure to treat according to randomization will be recorded in the subject's study records.

To maintain the balance between sites in terms of numbers of subjects randomized, study sites will be capped at randomizing a maximum of 15% of the overall study sample. Sites may be allowed to randomize beyond the cap on a case-by-case basis in consultation with the sponsor, taking into account overall study goals, randomization balances between sites, and prior quality of data collected by the site.

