11.3. Effectiveness Analysis

The primary effectiveness endpoint will be evaluated using the Win Ratio method (Pocock, et al., 2012) of analysis for a hierarchical composite endpoint based on the Finkelstein-Schoenfeld test (Finkelstein and Schoenfeld, 1999; Pocock, et al., 2012) with three components ranked in order of clinical importance: a) fatal perioperative bleeding events (occurring within 48hrs post-index procedure), b) moderate, severe, or massive perioperative bleeding events according to the Universal Definition of Perioperative Bleeding in Cardiac Surgery (UDPB) classification ≥ 2 , and c) 24-hour chest tube drainage (mL) following surgery. [9] [10] The Win Ratio assigns “wins”, “losses”, or “ties” in sequential comparisons between treatment and control arm subjects according to the hierarchical order of the components of the primary composite endpoint. There are two key advantages to the Win Ratio method of analysis. First, the hierarchical assessment of the individual components of the composite endpoint according to their clinical significance. Second, the opportunity for different types of components, such as categorical versus continuous, to all be included thereby capturing all available information from each component to increase statistical power. [9] The estimated Win Ratio along with a two-sided 95% CI will be provided between the treatment and control arm. The details of the primary effectiveness analysis will be provided in the SAP.

The key secondary effectiveness endpoint is a drug removal endpoint, namely the percent change in pre-CPB vs. post-CPB ticagrelor blood levels as measured by liquid chromatography/tandem mass spectrometry. Blood samples for drug removal analyses will be collected and analyzed by a central core laboratory.

Change from baseline in blood concentration of ticagrelor is defined as:

$$\frac{\text{pre-CPB [ticagrelor]blood} - \text{post-CPB [ticagrelor]blood}}{\text{pre-CPB [ticagrelor]blood}} * 100\%$$

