#### 3.3 Randomization/Blinding

All subjects will be randomized in a one to one (1:1) ratio to either the control arm (SoC) or the treatment arm (SoC + DrugSorb™-ATR device). Pre-randomization stratification will be performed by study site, and by type of intended surgical procedure - either:

- CABG alone (irrespective of number of grafts); or
- All other cardiothoracic procedures (including but not limited to combination procedures [i.e., CABG + aortic/mitral valve procedures, double heart valve procedures, etc.], aortic interventions, and combination aortic + cardiac interventions).

Of note, patients undergoing undergo CABG + minor add-on procedures (e.g., left atrial appendage clipping, IABP or Impella placement, etc.) that do not (in the opinion of the investigator) significantly increase operative complexity or bleeding risk are included in the CABG alone category for Type of planned cardiothoracic surgery. Please see Section 6.1 of the CIP for additional details of pre-randomization stratification. Randomization is implemented via an Interactive Voice/Web response (IxRS) system.

Neither the subjects nor the site personnel have the treatment assignment information during the study period, unless specified in **Section 6.3** of the CIP. The blinded study team is blocked from every subject's treatment assignment before the data base lock for unblinding. Please see **Section 6.3** of the CIP for additional details of study blinding.

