### **5.2.2.2 Win Ratio Estimates**

In order to evaluate the magnitude of treatment effect in the primary effectiveness endpoint, the unmatched win ratio estimates (Pocock 2012) will be provided as well as the corresponding 95% confidence interval (CI).

The unmatched win ratios are formed by comparing every subject in the treatment group with every subject in the control group. Specifically, if we let  $n, m$  be the number of subjects in the treatment and control groups, respectively, then we make  $n \times m$  paired comparisons. The win ratio is then calculated as  $N_W/N_L$  where  $N_W$  and  $N_L$  are the total number of pairwise wins and losses, respectively, for the treatment group.

Following Bebu (2016), logarithm of  $\widehat{WR} = N_W/N_L$  has an asymptotic normal distribution with mean and variance specified in (2.6) of the paper. Therefore, the estimated WR and the 95% Confidence Interval (CI) will also be derived and presented from the sample distribution of  $\log(\widehat{WR})$  using Delta method with the exponential transformation.

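### The primary Finkelstein-Schoenfeld test and win ratio ignore planned surgery type, a randomisation stratum the protocol ties to bleeding risk; this costs efficiency only, mainly if the true effect is smaller than planned

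*SAP*

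**What the plan says.** SAP 3.3: "Pre-randomization stratification will be performed by study site, and by type of intended surgical procedure". Protocol 6.2 gives the purpose: "To ensure even distribution of subjects among the factors most likely to impact the primary and secondary outcomes they will undergo pre-randomization stratification". Protocol 3 says of non-CABG surgery: "Compared to CABG-alone, these operations have a significantly different profile in regards to bleeding risk and procedure/CPB duration".

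The primary analysis does not use this factor. SAP 5.2.2.1 scores all pairs of subjects together and writes the variance with arm totals only, "where n and m are the sample size for the treatment and control group respectively". SAP 5.2.2.2 does the same for the estimate: "The unmatched win ratios are formed by comparing every subject in the treatment group with every subject in the control group". The bootstrap in SAP 5.2.3 changes only the variance estimate.

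Surgery type does appear elsewhere:
- Protocol 11.4 and SAP 3.6 present the primary endpoint and its components within CABG and other surgery. SAP 3.6 adds interaction models, built as in SAP 3.5, to judge consistency.
- SAP 5.2.4.3 repeats the primary analysis in isolated-CABG patients.
- SAP 5.4.1 and 5.4.1.1 analyse 24-hour chest tube drainage (CTD) by ANCOVA, with surgery type as a covariate where judged suitable. Protocol 11.3 specifies a two-sample t-test, with a nonparametric fallback.

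The protocol's amendment history for version 4.0 records: "Language around stratification of the Win Ratio analysis by study site and surgery type has been removed from Section 11.3". It gives no reason. Protocol 11.3 leaves the specifics to the SAP: "The details of the primary effectiveness analysis will be provided in the SAP".

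**The concern.** A factor important enough to stratify the randomisation is normally used in the analysis. If surgery type predicts bleeding, balancing it by design makes the arms more alike than the pooled variance allows for. The test then becomes conservative, and comparisons across surgery types add noise. The SAP is also uneven: it allows for surgery type when CTD is a secondary endpoint, but not when CTD is the third component of the primary.

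The planned uses of surgery type do not fill the gap. The isolated-CABG repeats drop the other-surgery patients, and the subgroup work assesses consistency. Neither gives one within-stratum test over all patients.

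At stake is power if the true effect falls short of plan. The CTD mismatch matters separately. CTD is third in the sequence of SAP 3.7 and gates platelet and red-cell transfusions, yet its confirmatory model is not fixed.

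**Working it through.** **Inputs from the documents** (SAP Table 1, Scenario 2): 65 per arm, two-sided 0.05; fatal bleeding 3.0% in both arms; UDPB ≥2 24.3% vs 40.5%; CTD 480 vs 800 mL, SD 500.

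**Assumed, because the documents give no figure:**
- Share of other surgery: 10%, 25% or 40%.
- Excess over CABG: none; moderate (+20 points UDPB ≥2, +200 mL); strong (+35 points, +400 mL).
- Whole-trial rates, means and SD held at the SAP values; components independent; permuted blocks of 4 within site and surgery type; 30 equal sites (the Synopsis says "Approximately 30 investigational sites in the US and Canada will participate in the study").
- CTD normal or lognormal. Normal CTD at 480 (500) implies about 17% negative volumes, so both shapes are shown.

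**Tests compared.** Pooled: T = Σ D_i W_i with variance nm/[N(N−1)] · Σ W_i². Stratified: the same T_s and V_s within each surgery stratum, then T = Σ_s T_s/(N_s+1) and Var = Σ_s V_s/(N_s+1)².

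**Reproducing the SAP.** The pooled test with normal CTD and no prognostic effect gives 91.9 to 92.1%, against 92.1% stated. Scenario 1 (57 per arm, SD 253) gives 99.5% against 99.7%; stratifying gains at most 0.3 point there.

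**Power, pooled → stratified (%), Scenario 2, same absolute effect in both strata, 20,000 trials per main cell:**

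| Effect, CTD shape | Prognosis | 10% share | 25% share | 40% share |
|---|---|---|---|---|
| Planned, normal | none | 92.1→91.8 | 91.9→91.7 | 91.9→91.6 |
| | moderate | 92.1→92.3 | 91.6→92.7 | 91.5→92.9 |
| | strong | 91.6→93.5 | 91.2→95.1 | 91.5→96.3 |
| Planned, lognormal | none | 98.8→98.6 | 99.1→99.0 | 98.9→98.8 |
| | moderate | 98.9→99.0 | 98.7→99.1 | 98.7→99.3 |
| | strong | 98.8→99.4 | 98.5→99.6 | 98.5→99.8 |
| 65%, normal | none | 57.1→56.7 | 57.1→56.7 | 57.5→57.1 |
| | moderate | 57.5→58.1 | 56.8→58.7 | 56.2→59.2 |
| | strong | 57.0→60.7 | 55.3→63.2 | 54.6→65.7 |
| 65%, lognormal | none | 76.6→76.1 | 76.6→76.1 | 77.1→76.7 |
| | moderate | 75.5→76.7 | 75.8→79.4 | 74.5→78.8 |
| | strong | 75.3→79.6 | 72.8→83.6 | 71.3→86.0 |

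**Type I error.** Stratified 4.8 to 5.2% throughout. Pooled 4.9 to 5.2% (none), 4.4 to 4.8% (moderate), 3.6 to 4.8% (strong); other runs of the strong case fell to about 3%.

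**Same absolute effect or same proportional effect?** Protocol Table 3 frames the effect as about a 40% reduction. In the strong case at a 25% share, control UDPB ≥2 in CABG is 40.5 − 0.25×35 = 31.75%. Subtracting 16.2 points is then a 51% reduction in that stratum (16.2/31.75). With a proportional 40% effect the strong-case gains at a 25% share are smaller: 2.2 to 2.4 points at plan (normal), and at 65% of plan 5.6 to 6.4 (normal) and 9.1 to 9.4 (lognormal), from runs of 3,000 to 4,000 trials per cell.

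**Overlap of components.** Twelve-hour drainage is part of UDPB. With correlation 0.5 between UDPB and CTD, gains at a 25% share (none/moderate/strong) are −0.5/+0.9/+4.2 at plan and −0.5/+1.2/+6.1 at 65% (normal), and −0.1/+0.3/+1.1 and −0.3/+2.6/+9.8 (lognormal).

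**Site.** Only 3.8% of cross-arm pairs fall within a site, against 0.75² + 0.25² = 62.5% within surgery type at a 25% share. Site-stratified power is 81.9 to 83.3% if site is not prognostic, and 89.5 to 90.1% under the largest site differences tried, against 90.8 to 92.1% pooled.

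**24-hour CTD, t-test → ANCOVA** (normal, strong, 25%/40% share): 95.9→97.0 and 95.5→97.4 at plan; 64.9→70.1 and 65.8→72.6 at 65%; essentially unchanged if surgery type is not prognostic.

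**The case against.** The pooled test is valid, fully specified and the basis of the sample size. Stratification was removed by a logged amendment, and restoring it changes the estimand of a pivotal trial after CTD variability had been seen (SAP 2). All of that stands, and it is why keeping the pooled primary is acceptable. The composite will also already be shown within both surgery types, so what is missing is narrow.

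The size of the gain rests on assumptions, including the 65% figure, and the largest gains need strong prognosis together with a reduced effect. That stands too. So does the point that the stratum is noisy: SAP 3.3 lets investigators class CABG with minor add-ons as CABG alone, and protocol 6.1 expects day-of-surgery changes.

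Site is also a stratum and is left out here. This is a trade-off: site leaves too few within-stratum pairs, whereas a two-level surgery factor does not.

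A reader might infer that the primary test is invalid, that the trial is underpowered, or that the version 4.0 removal was a mistake. The documents support none of these. The pooled test errs on the conservative side, its stated power reproduces, and the removal covered site and surgery type together with no reason given.

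**Conclusion.** The point holds as one of efficiency. A randomisation stratum the protocol calls important is absent from the primary test, and no planned analysis supplies a whole-population within-stratum test of the composite.

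At an assumed 25% share and SD 500:
- about 0.5 point of power or less is lost if surgery type is not prognostic;
- at the planned effect, about 0 to 1 point (moderate) or 1 to 5 points (strong) is gained, least with lognormal CTD, where pooled power already exceeds 98%;
- at 65% of the planned effect, about 1.5 to 3.5 points (moderate) or 5 to 11 (strong) is gained, towards the lower end if the effect is proportional.

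The protocol supports a prognostic effect only qualitatively, so which row applies is unknown. The CTD discrepancy needs no assumption: the two documents name different models for a confirmatory test, and the SAP's covariate is conditional on an unstated criterion.

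**What to change.** Before unblinding, and documented as decided while blinded, amend SAP 5.2.2.1 along these lines:

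> In the mITT, ITT and PP sets the Finkelstein-Schoenfeld test is stratified by planned surgery type as entered in IxRS (CABG alone; all other). Pairs are formed within stratum. T = Σ_s T_s/(N_s+1) and Var = Σ_s V_s/(N_s+1)². A stratum with an empty arm contributes nothing. The isolated-CABG sets use the unstratified test.

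State the weights: summing strata unweighted lost up to 5.3 points in one non-prognostic case (half the planned effect, SD 253, 20% share).

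In SAP 5.2.2.2 report the matching within-stratum win ratio, [Σ_s N_W,s/(N_s+1)] / [Σ_s N_L,s/(N_s+1)], with a delta-method interval. Resample within arm and stratum in 5.2.3, and apply the same rules to the UDPB ≥3 composite in 5.2.5. Keep the pooled test and unmatched win ratio as pre-specified sensitivity analyses. Do not stratify by site.

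Acceptable alternative: keep the pooled test as primary, state why, and pre-specify the stratified test with these weights as a sensitivity analysis.

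For 24-hour CTD, reconcile protocol 11.3 with SAP 5.4.1 and 5.4.1.1 and name one confirmatory model. If ANCOVA stays, make the covariate unconditional: planned surgery type in the mITT and PP sets, omitted in the isolated-CABG sets.

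Costs:
- No new data are needed, only SAP text and code, but the change reverses part of a logged amendment.
- Up to about 0.5 point of power is lost if surgery type is not prognostic.
- The win ratio becomes a within-stratum quantity (40% share, strong: 1.96 to 2.17 with normal CTD, 2.28 to 2.79 with lognormal).
- Misclassification dilutes the gain. If 10% of patients have surgery other than planned, the strong-case gain at a 25% share falls from 3.8 to 2.4 points at plan (normal), and at 65% from 8.0 to 5.6 (normal) or 10.8 to 7.5 (lognormal). Add-on procedures classed as CABG alone act in the same direction.
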